4.1.2 Definition of dose-limiting toxicities and stopping criteria

Dose-limiting toxicities will be determined during Cycles 1 and 2 of the dose-finding phase using CTCAE version 5. Toxicities that occur during the first 28 day cycle and meet the criteria below will be assessed for attribution to durvalumab monotherapy. Any of the below listed AEs encountered between Cycle 1 Day 1 and Cycle 2 Day 28 (ie, 56 day DLT monitoring period for combination therapy) and in the opinion of the Investigator is thought to be attributable to durvalumab or/and tremelimumab, given a reasonable possibility based on temporal exposure to IP and for which an alternate etiology does not exist or cannot be identified, will be classified as DLTs:

- Grade 5 toxicity
- Hematological toxicity: Any Grade ≥ 3 (including febrile neutropenia Grade ≥ 3) except for the following:
 - Grade 3 thrombocytopenia that does not result in a bleeding event or does not require platelet transfusion
 - Grade 3 neutropenia that resolves to Grade ≤ 2 within 7 days.
- Non-hematological toxicity:
 - Any Grade 4 imAE
 - Any \geq Grade 3 colitis
 - Any Grade 3 or 4 noninfectious pneumonitis
 - Any Grade 2 pneumonitis that does not resolve within 5 days to \leq Grade 1 after initiation of maximal supportive care (including use of steroids)
 - Any Grade 3 imAE, excluding colitis or pneumonitis, that does not downgrade to Grade 2 within 3 days after onset of the event despite optimal medical management including systemic corticosteroids and does not downgrade to \leq Grade 1 or baseline within 14 days of onset
 - Liver transaminase elevation $>5 \times$ upper limit of normal (ULN) or total bilirubin (TBL) $>3 \times$ ULN. For patients with liver metastases at baseline, transaminase elevation $>8 \times$ ULN will constitute a DLT
 - Grade 4 vomiting, diarrhea, electrolyte abnormality, or systemic reaction
 - Grade 3 toxicity lasting >7 days despite optimal supportive care
 - Any \geq Grade 3 non-imAE, except for the exclusions listed below
 - Any Grade 3 immune-mediated peripheral neuropathy or other immune-mediated neurotoxicity
 - Grade ≥ 3 inflammatory reactions.

The definition of DLTs excludes the following conditions:

- Grade 3 fatigue lasting ≤ 7 days.
- Grade 3 endocrine disorder (pituitary and/or adrenal insufficiency) that is managed with or without systemic corticosteroid therapy and/or hormone replacement therapy and the patient is asymptomatic.
- Grade 3 hypothyroidism adequately treated with hormone replacement therapy.
- Grade 3 inflammatory reaction attributed to a local antitumor response (eg, inflammatory reaction at sites of metastatic disease, lymph nodes, etc.).
- Concurrent vitiligo or alopecia of any AE grade.
- Grade 3 infusion-related reaction (first occurrence and in the absence of steroid prophylaxis) that resolves within 6 hours with appropriate clinical management.
- Grade 3 fever (fever greater than 40°C [$>104^{\circ}\text{F}$] for $\leq 24\text{h}$ in duration).
- Any grade lymphopenia.
- Isolated Grade 3 electrolyte abnormalities that are not associated with clinical signs or symptoms and are reversed with appropriate maximal medical intervention (including supplementation) within 7 days of initiating supplementation.

Immune-related adverse events are defined as AEs of immune nature (ie, inflammatory) in the absence of a clear alternative etiology. In the absence of clinical abnormality, repeat laboratory testing must be conducted to confirm significant laboratory findings prior to designation as a DLT.

Guiding principles:

1. While the rules outlined above dictate the classification of AEs as DLTs, any other AEs that are observed during the observation period may be defined as a DLT in consultation with the DRC; after having taken into consideration the emerging safety profile of durvalumab and tremelimumab.
2. The NCI CTCAE (version 5.0) will be used for AEs reporting and its severity will be graded on a scale from 1 to 5 provided for each AE term.
3. An immune-mediated AE is defined as an AE that is associated with exposure to durvalumab or/and tremelimumab and is consistent with an immune-mediated mechanism of action after alternate etiologies have been considered and excluded.

4. In the absence of clinical findings, repeat laboratory testing must be conducted to confirm the clinical significance of abnormal laboratory test result before it is classified as a DLT.

Patient dosing or study enrollment may be halted in the dose-finding phase until the toxicity data can be further studied. If DLTs occur in $\geq 2/6$ patients on a given cohort, enrollment will be placed on hold and the DRC will be required to fully evaluate the available information prior to further patient enrollment. Upon review, a decision will be made to resume, stop or modify the study. If ≥ 2 DLTs occur at DL -1, the study may be prematurely stopped.

In the dose-expansion phase, enrollment in a disease-specific cohort will be halted and the DRC will be required to fully evaluate the available information prior to further patient enrollment if $\geq 3/9$ patients have an AE or SAE that would be considered a DLT based on criteria established in the dose-finding phase. Upon review, a decision will be made to resume, stop or modify the study.

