2.3.2.1 Durvalumab

Risks with durvalumab include, but are not limited to, diarrhea/colitis, pneumonitis/ILD, endocrinopathies (ie, events of hypophysitis, adrenal insufficiency, hyper- and hypo-thyroidism, and type I diabetes mellitus), hepatitis/increases in transaminases, nephritis/increases in creatinine, pancreatitis, rash/dermatitis (including pemphigoid), myocarditis, myositis/polymyositis, encephalitis; other rare or less frequent inflammatory events including immune thrombocytopenia and neuromuscular toxicities (eg, Guillain-Barré syndrome, myasthenia gravis), infusion-related reactions, hypersensitivity reactions, and infections/serious infections.

For information on all identified and potential risks with durvalumab, please always refer to the current version of the durvalumab IB.

In monotherapy clinical studies, AEs reported very commonly include events such as fatigue, diarrhea, nausea and vomiting, decreased appetite, and muscle and joint pain. As of 03 November 2017, a total of 5% to 10% of adult patients discontinued the drug due to an AE. Please see the current version of the IB for a detailed and updated summary of the monotherapy data including AEs, serious adverse events (SAEs), and National Cancer Institute (NCI)

Common Terminology Criteria for Adverse Events (CTCAE) Grade 3 to 5 events reported across the durvalumab program.

The majority of treatment-related AEs were manageable, with dose delays, symptomatic treatment, and in the case of events suspected to have an immune basis, the use of established treatment guidelines for immune-mediated toxicity (see Section 8.4.5).

From review of the ongoing CCI study, there were no new safety risks identified (see Section 2.2.2).

A detailed summary of durvalumab monotherapy AE data can be found in the current version of the durvalumab IB.

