4.1.3 Determining a recommended Phase II dose

A DRC will be established prior to the initiation of the study to review all the data, with a primary emphasis on safety and PK, to establish RP2D to be further explored in the dose-expansion phase of the study. Dose escalation decisions and determination of RP2D will mainly consider safety assessments from at least 3 patients followed up for 4 cycles, to include a single cycle of durvalumab and 3 cycles of the combination of durvalumab and tremelimumab (for a total of 120 days). More details on the DRC constitution are described in Section 9.6.1.

The key considerations to be followed by the DRC during the dose-finding phase of the study are outlined in [Table 8](#).

Table 8 Key considerations for dose escalation decisions

#DLTs	Pharmacokinetics	Decision/Outcome
0 out of 3-5	Equivalent to adult exposure (5 out of 6 patients) Less than 80% of adult exposure (≤ 2 patients)	Declare tolerated and observe for 4 cycles, and if < 2 patients with DLTs are observed during the first 4 cycles of study drug, enter dose-expansion stage Declare tolerated and move to next DL
OR 1 out of 6		
1 out of 3		Increase number of patients to 6
≥ 2		Declare not tolerated; if observed on DL 1, move to DL -1

DL Dose level; DLT Dose-limiting toxicity.

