9.6.1 Data Review Committee

A DRC will be established prior to the initiation of the study and will review the safety and PK data. The DRC membership will comprise of participating Investigators and representatives from both AstraZeneca (Pharmacovigilance Scientists for durvalumab and tremelimumab, PK Scientist, Study Physician and Biostatistician) and IQVIA (Study Physician, Safety Physician and Biostatistician). On a case-by-case basis, the DRC may also seek advice from pediatric oncologists with the required site specialization expertise.

Working rules, including the timing of planned meetings, will be described in the DRC charter. In summary, recommendations and decisions will be made through consensus of opinion amongst the DRC members with all decisions being documented and distributed to DRC members. Additionally, 'ad-hoc' DRC meetings may be convened, if required, anytime during the conduct of the study.

The key tasks of the DRC members will be to review the data recorded in the clinical database in conjunction with the PK data to:

1. Determine whether DLTs have occurred
2. Decide whether additional patients should be added to a cohort
3. Recommend de-escalating a dose that was poorly tolerated or escalating a dose if PK exposures inferior to those observed in adults, were achieved
4. Declare that dose finding is complete

5. Recommended a RP2D to be explored in the dose-expansion phase of the study
6. Perform a benefit/risk assessment at the completion of safety data analysis for children <1 year old prior to enrolling a patient less than 1 year old; notify local health authority of decision, if applicable, as per local requirements
7. Put enrollment on hold
8. End the study.

During the dose-expansion phase, the DRC will review safety, tolerability, PK, and efficacy data to make consensual decisions on cohort expansion or closure, and end the study, among others.

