- Grade 3 inflammatory reaction attributed to a local antitumor response (eg, inflammatory reaction at sites of metastatic disease, lymph nodes, etc.).

- Concurrent vitiligo or alopecia of any AE grade.
- Grade 3 infusion-related reaction (first occurrence and in the absence of steroid prophylaxis) that resolves within 6 hours with appropriate clinical management.
- Grade 3 fever (fever greater than 40°F for ≤24h in duration).
- Any grade lymphopenia.
- Isolated Grade 3 electrolyte abnormalities that are not associated with clinical signs or symptoms and are reversed with appropriate maximal medical intervention (including supplementation) within 7 days of initiating supplementation.

irAEs are defined as AEs of immune nature (ie, inflammatory) in the absence of a clear alternative etiology. In the absence of clinical abnormality, repeat laboratory testing must be conducted to confirm significant laboratory findings prior to designation as a DLT.

Guiding principles:

1. While the rules outlined above dictate the classification of AEs as DLTs, any other AEs that are observed during the observation period may be defined as a DLT in consultation with the DRC; after having taken into consideration the emerging safety profile of durvalumab and tremelimumab.
2. The NCI CTCAE (version 5.0) will be used for AEs reporting and its severity will be graded on a scale from 1 to 5 provided for each AE term.
3. An immune-mediated AE is defined as an AE that is associated with exposure to durvalumab or/and tremelimumab and is consistent with an immune-mediated mechanism of action after alternate etiologies have been considered and excluded.
4. In the absence of clinical findings, repeat laboratory testing must be conducted to confirm the clinical significance of abnormal laboratory test result before it is classified as a DLT.

For reporting purposes, the DLTs are as approved and documented at the DRC meetings.

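### As worded, Grade 3 thrombocytopenia is a DLT only if bleeding and platelet transfusion both occur; a bleed below Grade 3 alone, or a transfusion alone, is exempt unless the DRC adds it

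*Protocol*

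**What the plan says.** Protocol 4.1.2 makes every haematological toxicity of Grade 3 or higher a DLT and then lists two exceptions. The first is "Grade 3 thrombocytopenia that does not result in a bleeding event or does not require platelet transfusion". SAP 3.3.6 carries the identical bullet, so neither document corrects the other.

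The classification feeds three decisions:

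- **Tolerability (Protocol 4.1.3, Table 8).** Two or more DLTs lead to "Declare not tolerated; if observed on DL 1, move to DL -1".
- **Dose-finding hold (Protocol 4.1.2).** Enrolment goes on hold, pending DRC evaluation, once 2 of 6 patients in a cohort have a DLT.
- **Expansion hold (Protocol 4.1.2).** Enrolment in a disease-specific cohort is halted for DRC evaluation if at least 3 of 9 "patients have an AE or SAE that would be considered a DLT based on criteria established in the dose-finding phase".

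Protocol 9.6.1 gives the DRC the task to "Determine whether DLTs have occurred". SAP 3.3.6 adds: "For reporting purposes, the DLTs are as approved and documented at the DRC meetings". Guiding principle 1 in Protocol 4.1.2 says that "any other AEs that are observed during the observation period may be defined as a DLT in consultation with the DRC".

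**The concern.** An exception of this kind is normally meant for uncomplicated laboratory events: a low platelet count with no clinical consequence. The bullet reads as if it was meant that way. However, it links two complete negative clauses with *or*, so a patient who needed platelets but did not bleed meets one clause and is exempt. So is a patient who bled but was not transfused.

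The event is foreseeable. Protocol 2.3.2.1 lists among the durvalumab risks "other rare or less frequent inflammatory events including immune thrombocytopenia", and Protocol 2.3.2.2 names thrombocytopenia among the cytopenias seen with tremelimumab.

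At stake is a safety review that is not triggered when a complicated event should have counted towards it.

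**Working it through.** There is no sample size, power or error rate to reproduce. The check is of the rule's logic and then of its effect on the thresholds.

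**1. Truth table.** Let B = a bleeding event and T = platelet transfusion required, for Grade 3 thrombocytopenia that is attributable and falls in the window.

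- As written: exempt if (not B) or (not T). The event is therefore a DLT only if B and T.
- Read as *neither*: exempt if (not B) and (not T). The event is therefore a DLT if B or T.

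| Bleed | Transfusion | As written | *Neither* reading |
|---|---|---|---|
| No | No | Exempt | Exempt |
| No | Yes | Exempt | DLT |
| Yes | No | Exempt | DLT |
| Yes | Yes | DLT | DLT |

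The readings differ in the two middle rows only.

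**2. What other bullets already catch.** Grade 4 thrombocytopenia is never exempt, because the exception covers Grade 3 only. An attributable bleed of Grade 3 or above is a DLT in its own right, under the bullet for non-immune-mediated events of at least that grade. Removing those cases leaves:

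- a bleed below Grade 3 without transfusion;
- a transfusion without a bleed.

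The bullets on Grade 3 toxicity lasting more than 7 days and on Grade 3 immune-mediated events that fail to improve sit under the non-haematological heading. As laid out, they do not reach the thrombocytopenia. If they were read more widely, they would turn on duration or failure to downgrade, not on bleeding or transfusion.

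**3. Wording elsewhere in the list.** The Grade 3 immune-mediated bullet covers an event that does not fall to Grade 2 within 3 days "despite optimal medical management including systemic corticosteroids and does not downgrade to" Grade 1 or baseline within 14 days. There, two negative conditions are joined by *and*. A reader comparing the bullets has no reason to give *or* anything but its ordinary meaning.

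**4. Effect on the thresholds of one uncounted event.**

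- Dose-finding: 2/6 = 33.3% becomes 1/6 = 16.7%, below both the hold and the not-tolerated row.
- Expansion: 3/9 = 33.3% becomes 2/9 = 22.2%, below the hold.

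**5. Illustration with assumed rates.** The rates here are not in the documents. With six patients and DLT probability p, the chance of reaching two or more is 1 − (1 − p)^6 − 6p(1 − p)^5. Let single-complication cases add 0, 2, 5 or 10 percentage points to the DLT rate that the literal rule gives.

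| Literal DLT rate | +0 | +2 | +5 | +10 |
|---|---|---|---|---|
| 10% | 0.114 | 0.156 | 0.224 | 0.345 |
| 20% | 0.345 | 0.394 | 0.466 | 0.580 |

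The difference is small if these cases are rare and becomes material only if they are common.

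**The case against.** The best reply is that clinicians do not read protocol prose as Boolean algebra. In a list of exceptions for uncomplicated events, most would understand *neither*. Nothing in the documents shows that any site or the DRC would exempt a complicated case. That is fair as to intent, but it is also a reason to make the text say it. The comparison with the immune-mediated bullet is supporting evidence only, since that bullet includes events and this one exempts them.

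Second, the count is not the only route to a review. Dosing or enrolment in dose-finding may be halted without any DLT threshold. The DRC decides what is a DLT, may add other events, can hold enrolment or meet ad hoc, and reviews safety during expansion. This stands and limits the damage, including variation between sites. But the DRC would be applying this same text, and its power to add is permissive. Guiding principle 1 refers to the observation period; whether it extends to the expansion hold is not stated.

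Third, the version history (Version 2.0) records that the DLT parameters were revised after discussion with the FDA, and whether one complication should be dose-limiting is a clinical judgement. That history does not show that the *or* was deliberate.

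Fourth, it is late. The version history suggests expansion was already under way, Protocol 4.1 put the last visit for the final analysis in Q1 2023, and the latest SAP revision is dated 19 April 2023. Little prospective use may remain. This is accepted and is one reason the point is minor.

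**Conclusion.** The concern holds: the bullet is wrong as written, at minor severity. Taken literally, it exempts Grade 3 thrombocytopenia with a bleed below Grade 3 alone or with a transfusion alone, and no other listed criterion reliably brings those cases back.

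How many patients this affects cannot be estimated, because neither document gives a rate. The threshold effect matters only when the omitted event is the one that would have reached 2 of 6 or 3 of 9. Even then, what is lost is a mandatory DRC review, not an automatic stop. The main remaining use of the rule is the expansion hold, plus any further dose decision.

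The conclusion assumes that the event is attributed to study drug with no alternative cause and, for a dose-finding DLT, that it falls within the 56-day window. It also assumes that the non-haematological bullets apply only under their own heading.

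**What to change.** In Protocol 4.1.2 and SAP 3.3.6, replace the bullet with: *Grade 3 thrombocytopenia that neither results in a bleeding event nor requires platelet transfusion*. Either complication alone then makes the event a DLT for dose decisions and a DLT-type event for the expansion hold.

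The drafting cost is one bullet in each document, with no new data collection. The protocol change has to go through the usual regulatory and ethics approval, so it is best carried in an amendment made for other reasons. Slightly more events will count.

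If dose-finding is closed, a short DRC note should state which reading was applied and whether any single-complication case occurred. This would settle the reported DLT counts and show whether the expansion hold is being judged on the same basis as the recommended dose.

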4.1.3 Determining a recommended Phase II dose

A DRC will be established prior to the initiation of the study to review all the data, with a primary emphasis on safety and PK, to establish RP2D to be further explored in the dose-expansion phase of the study. Dose escalation decisions and determination of RP2D will mainly consider safety assessments from at least 3 patients followed up for 4 cycles, to include a single cycle of durvalumab and 3 cycles of the combination of durvalumab and tremelimumab (for a total of 120 days). More details on the DRC constitution are described in Section 9.6.1.

The key considerations to be followed by the DRC during the dose-finding phase of the study are outlined in [Table 8](#).

Table 8 Key considerations for dose escalation decisions

#DLTs	Pharmacokinetics	Decision/Outcome
0 out of 3-5	Equivalent to adult exposure (5 out of 6 patients) Less than 80% of adult exposure (≤ 2 patients)	Declare tolerated and observe for 4 cycles, and if < 2 patients with DLTs are observed during the first 4 cycles of study drug, enter dose-expansion stage Declare tolerated and move to next DL
OR 1 out of 6		
1 out of 3		Increase number of patients to 6
≥ 2		Declare not tolerated; if observed on DL 1, move to DL -1

DL Dose level; DLT Dose-limiting toxicity.

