At least 1 patient representing each of the following pediatric age subsets will be enrolled: birth to 5 years, 6 to 11 years and 12 to < 18 years. However, patients under 2 years of age will only be enrolled after at least 3 pediatric patients older than 2 years of age have been dosed with durvalumab and tremelimumab and have cleared the DLT observation period and have been evaluated by the DRC. Additionally, at least 1 day between first patient and subsequent patients dosed at each DL is required.

Three DLs may be explored in each of the treatment arms (detailed DLs can be seen in [Table](#) , [Table 11](#), [Table 12](#), and [Table 13](#)). The starting doses (DL 1) will be 100% of the recommended adult dose of both durvalumab and tremelimumab administered as weight-adjusted doses. The doses and schedules are as follows:

1. Cycle 1 (durvalumab monotherapy): durvalumab 20 mg/kg
2. Cycles 2 to 5 (durvalumab in combination with tremelimumab): durvalumab 20 mg/kg and tremelimumab 1 mg/kg (4 cycles administered every 28 days)
3. From Cycle 6 onwards, treatment will continue until a discontinuation criterion is met, with durvalumab monotherapy administered at 20 mg/kg every 28 days.

From Cycle 2 onwards, a treatment delay of up to 14 days is permitted between consecutive cycles to manage any side-effects. If a treatment delay of more than 14 days is required, the start of the cycle that had to be delayed must be skipped until the planned Day 1 of the next cycle. No dose reductions are permitted.

[figure not shown]
The pediatric PK will be considered equivalent to the adult PK when the lower limit of the 80% CI of the pediatric exposure (as measured by the area under the plasma drug concentration-time curve from Day 0 to Day 28 [AUC_{0-28}]) is more than 50% of the adult exposure. Adequate exposure will be declared only if $\geq 80\%$ (5 of 6 patients at a dose level) achieve acceptable adult exposure PK, as defined. Durvalumab and tremelimumab will be escalated sequentially with durvalumab first followed by tremelimumab.

The degree of dose escalation at DLs 2 and 3 will be determined based on the review of all the safety and emerging PK data. It is anticipated that dose ranges of 24 to 40 mg/kg and 1.2 to 2 mg/kg for durvalumab and tremelimumab, respectively, will be explored in DLs 2 and 3 (the maximum dose of durvalumab that will be explored is 40 mg/kg).

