Dose escalation will follow a modification of the standard 3 + 3 design. For Arm A (weight ≥ 35 kg), a total of 6 patients will be enrolled into this cohort; additional dose levels will only be evaluated if PK data indicate inadequate exposure to that of an adult. For Arm B (weight < 35 kg), if none of the 3 patients experience a DLT, then 3 additional patients will be treated at the next dose level. If 1 or more patients experience a DLT, the 3 additional patients (for a total of 6 patients) will be treated at the same dose level. Dose escalation will continue using the same rules-based approach until at least 2 patients among a cohort of 3 or 6 patients experience a DLT, at which time, DLT will be established.

Figure 2 Dose-finding: escalation schema

This figure shows the maximum doses for durvalumab at DLs 2 and 3 (40 mg/kg) and tremelimumab at DL 3 (2 mg/kg). Lower doses may be tested, depending on the obtained PK modeling data.

DL Dose level; NB Neuroblastoma; SARC-1 Osteosarcoma and Ewing sarcoma; SARC-2 Rhabdomyosarcoma, non-rhabdomyosarcoma, and other sarcomas; STO Solid tumor other.

As indicated in [Figure 2](#), DL 2 will assess an increased dose of durvalumab while holding tremelimumab dosing at 1 mg/kg.

[figure not shown]
If at DL 1, durvalumab exposure is adequate and tremelimumab exposure is too low, DL 2 can be skipped and tremelimumab alone will be escalated to DL 3 with durvalumab dosing staying at 20 mg/kg (100% of the recommended adult dose).

Furthermore, based on emerging PK, safety and tolerability data, intermediate DLs may also be tested.

De-escalation for toxicity may occur for durvalumab or tremelimumab to DL -1 with reduced doses of 15 mg/kg and 0.75 mg/kg, respectively (See [Figure 3](#)).

Figure 3 Dose-finding: de-escalation schema

DL Dose level

Assessments

During Cycle 1 and until Cycle 2 (Day 1), safety, tolerability, PK, and activity will be assessed as follows:

1. Encountered AEs will be reported and DLTs (defined in Section 4.1.2) will be identified
2. Four durvalumab PK samples (taken predose and end-of -infusion on Day 1 and on Day 8 and Day 15) will be obtained and
3. Three samples will be taken on Day 1 (pre- and postdose) and Day 8 to determine CCI.

During Cycle 2, safety, tolerability, PK, and activity will be assessed as follows:

1. Encountered AEs will be reported and DLTs will be identified
2. Two durvalumab PK samples (taken predose and at the end of infusion on Day 1) will be obtained

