4.3 Justification for dose

4.3.1 Durvalumab and tremelimumab dose and treatment regimen justification

4.3.1.1 Durvalumab + tremelimumab combination therapy dose rationale

The durvalumab + tremelimumab combination therapy doses and regimen selected for this study are based on the goal of selecting an optimal combination dose of durvalumab and tremelimumab that would yield sustained CCI demonstrate promising efficacy, and have an acceptable safety profile.

Pharmacokinetics/Pharmacodynamics data

Durvalumab:

Study patients will initially receive the recommended adult weight-adjusted dose of 20 mg/kg IV durvalumab q4w (maximum durvalumab dose to be explored is 40 mg/kg). Based on the simulations and preliminary PK results from study CCI, children ≥ 35 kg are predicted to have exposure levels consistent with adult patients. However, simulations also indicated that patients < 35 kg in weight are expected to have approximately 2 to 10-fold lower exposure than those observed in adults depending on weight. The minimum acceptable AUC_{0-28} for this

pediatric population is 50% of the adult AUC (3233-day \times $\mu\text{g/mL}$). The systemic exposure in children will be considered adequate if the lower 80% confidence bound on estimated AUC_{0-28} at the current DL is higher than 3233-day \times $\mu\text{g/mL}$. If lower exposures are confirmed, escalations defined in Section 4.1.1 will take place, and PK assessments will take place to confirm that exposure levels similar to adults are achieved.

Tremelimumab:

Children and young adults will initially receive the recommended adult weight-adjusted dose of 1 mg/kg IV tremelimumab q4w. Based on the simulations, children ≥ 35 kg are predicted to have exposure levels consistent with adult patients. However, simulations also indicated that patients < 35 kg in weight are expected to have approximately 2 to 4-fold lower exposure than those observed in adults. AUC_{0-28} will be used to determine adequacy of systemic exposure. The minimum acceptable AUC_{0-28} for this pediatric population is 50% of the adult AUC, or 137-day \times $\mu\text{g/mL}$. The systemic exposure will be considered adequate if the lower 80% confidence bound on estimated AUC_{0-28} at the current DL is greater than 137-day \times $\mu\text{g/mL}$. If lower exposures are confirmed, escalations defined in Section 4.1.1 will take place, and new assessments will take place to confirm that exposure levels similar to adults are achieved.

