A Data Review Committee (DRC) will be established prior to the initiation of the study to make decisions on dose escalations and determination of a recommended phase 2 dose (RP2D) to be further explored in the dose-expansion phase.

Dose escalation decisions will aim to identify the RP2D for durvalumab and tremelimumab in combination. Dose escalation decisions and determination of RP2D will mainly consider safety and PK information obtained from Cycle 1 (durvalumab monotherapy) and Cycle 2 (first administration of durvalumab and tremelimumab combined). This includes assessment of pre-defined dose-limiting toxicities (DLTs) in the first 2 cycles.

A de-escalation step may occur for durvalumab or/and tremelimumab, with reduced doses of 15 mg/kg and 0.75 mg/kg, respectively, if dose level 1 is considered not tolerated. Furthermore, if exposure of durvalumab or/and tremelimumab proves inadequate, intermediate dose levels may also be tested.

At least 1 patient representing each of the following pediatric age subsets will be enrolled: birth to 5 years, 6 to 11 years and 12 to <18 years. In addition, 3 patients older than 2 years of age must be treated with durvalumab in combination with tremelimumab and clear the DLT period and have been evaluated by the DRC before children less than 2 years old may be enrolled in the dose-finding phase.

[figure not shown]
The key considerations to be followed by the DRC during the dose-finding phase of the study are outlined in [Table 1](#):

Table 1 Key considerations for DRC

#DLTs	PK	Decision/Outcome
0 out of 3-5	Equivalent to adult exposure (5 out of 6 patients)	Declare tolerated and observed for 4 cycles, and if <2 patients with DLTs are observed during the first 4 cycles of study drug, enter dose-expansion stage
OR		
1 out of 6	<80% of adult exposure (≤2 patients)	Declare tolerated and move to next dose level.
1 out of 3		Increase number of patients to 6.
≥2		Declare not tolerated; if observed on dose level 1, move to dose level -1 (see Figure 2).

DLT dose limiting toxicity; DRC data review committee; PK pharmacokinetics.

Figure 2 Dose-finding: de-escalation schema

DL dose level.

A separate document (a DRC charter) will be created to detail all key tasks, working rules and timing of meetings of the DRC committee.

Dose-expansion phase

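### The dose-escalation tables print an 80%-of-adult-exposure trigger that conflicts with the 50% criterion and the 5-of-6 rule in the protocol text

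*Protocol*

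**What the plan says.** Protocol 4.1.1 treats pediatric PK as equivalent to adult PK when "the lower limit of the 80% CI of the pediatric exposure", measured as AUC0-28, "is more than 50% of the adult exposure". Exposure is then declared adequate only if at least 80% of patients qualify, spelled out as "5 of 6 patients at a dose level) achieve acceptable adult exposure PK, as defined". Section 4.3.1.1 repeats the floor in absolute terms. For durvalumab, the minimum acceptable value for this "pediatric population is 50% of the adult AUC (3233-day" × μg/mL). For tremelimumab it is 137 in the same units.

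Table 8 in protocol 4.1.3 and Table 1 in SAP 1.2 turn this into decisions for the Data Review Committee (DRC). They hold two PK entries. Equivalence in 5 of 6 patients leads to further observation and then expansion. The other entry reads "Less than 80% of adult exposure" in the protocol and "<80% of adult exposure" in the SAP, each with a bracketed count of at most 2 patients, and leads to the next dose level.

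The arm-specific text in 4.1.1 differs by weight. For Arm A (35 kg and over), "additional dose levels will only be evaluated if PK data indicate inadequate exposure to that of an adult". For Arm B (under 35 kg), "if none of the 3 patients experience a DLT, then 3 additional patients will be treated at the next dose level"; that sentence does not mention PK.

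SAP 3.4.1 names PK parameters as the primary endpoint of dose-finding. SAP 4.2.4.1 plans descriptive AUC statistics and no count of patients who meet the 50% criterion.

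**The concern.** A trigger at 80% of adult exposure appears only in these two table cells. In every other PK rule, 80% is either a confidence level or a share of patients. The tables are what the DRC is told to follow when it decides between escalating and stopping, so a wrong threshold there bears on the primary dose-finding objective, adult-equivalent exposure, and on the RP2D given to every expansion patient. The count of at most 2 patients has no stated denominator, and neither table says whether it counts patients with adequate or with inadequate exposure. The planned outputs would not let a reader of the CSR see which criterion was applied.

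**Working it through.** **Inputs.** Floor of 50% of adult AUC0-28: 3233 (durvalumab) and 137 (tremelimumab), protocol 4.3.1.1. Share required: at least 80%, given as 5 of 6, protocol 4.1.1. Table trigger: below 80% of adult exposure, at most 2 patients, protocol Table 8 and SAP Table 1.

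**Step 1: reproduce the plan's own figure.** The smallest count that makes 80% of n is 0.80 × n rounded up. For n = 6, 0.80 × 6 = 4.8, so 5 are needed (5/6 = 83.3%; 4/6 = 66.7% fails). This matches 5 of 6.

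**Step 2: the two exposure thresholds.** Adult AUC is 3233/0.5 = 6466 for durvalumab and 137/0.5 = 274 for tremelimumab. Eighty percent of these is 0.8 × 6466 = 5173 and 0.8 × 274 = 219. Read literally, the tables therefore use 5173 and 219 where the text uses 3233 and 137.

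**Step 3: the complement of the 80% rule by cohort size.**

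| Patients n | 0.80 × n | Fewest that reach 80% | Below 80% if at most |
|---|---|---|---|
| 3 | 2.4 | 3 | 2 |
| 4 | 3.2 | 4 | 3 |
| 5 | 4.0 | 4 | 3 |
| 6 | 4.8 | 5 | 4 |

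At most 2 is right only for n = 3. This supports reading the cell as a shortened form of fewer than 80% of patients, written for a cohort of 3. For n = 6 it should be at most 4.

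**Step 4: which outcomes have a table row.**
- If the count means patients with adequate exposure: at n = 6, 0 to 2 lead to the next level, 5 or 6 lead to expansion, and 3 or 4 have no row. At n = 3, 3 of 3 has no row.
- If it means patients below target: at n = 6, 5 adequate (1 below) fits both entries, 4 adequate (2 below) leads to the next level, and 0 to 3 adequate have no row.

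Neither reading reproduces the rule of 4.1.1 at n = 6.

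**Step 5: how often the gap would arise on the first reading.** The documents give no per-patient probability p of adequate exposure, so p is assumed over a range. P(3 or 4 of 6) = 20p³(1−p)³ + 15p⁴(1−p)². For p = 0.2, 0.3, 0.4, 0.5, 0.6, 0.7, 0.8 and 0.9 this is 0.10, 0.24, 0.41, 0.55, 0.59, 0.51, 0.33 and 0.11.

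**Step 6: when a smaller cohort can still reach 5 of 6.** With k adequate of n, the most that 6 patients can give is k + (6 − n). This is at least 5 when k ≥ n − 1, so 5 of 6 is still open from 2 of 3, 3 of 4 and 4 of 5, as well as from 3 of 3, 4 of 4 and 5 of 5.

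**The case against.** The strongest reply is that the plan's text already supplies most of the rule.
- Section 4.1.1 allows adequacy only at 5 of 6, so 3 or 4 of 6 is inadequate whatever the table omits. For Arm A the text then leads to a further level.
- The third DRC task in 9.6.1 ties escalation to exposures inferior to those in adults, for both arms.
- The planned totals, 12 = 1 level × 2 arms × 6 and 36 = 3 levels × 2 arms × 6, imply six patients per level per arm.
- The tables are key considerations for a committee that decides by consensus. Its charter, which is not among the documents, may hold the working rule. SAP section 6 shows that the charter does hold definitions.

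All of this stands, and it limits the fault to the tables and one sentence. A reader might infer that Arm B escalated with no regard to PK. The documents do not support that, because the DRC task applies to both arms; what is true is that the Arm B sentence does not refer to the condition, and the DRC task gives no threshold or count. A reader might also infer that one cohort could often qualify for expansion and escalation at once. That needs the literal reading of a cell that is probably garbled, and its frequency depends on exposure levels, variability and confidence-interval widths that the documents do not give. Nor should weight be put on how the DLT rows line up with the 5-of-6 entry, since the layout may come from a merged cell.

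**Conclusion.** The table trigger is wrong as written and should be corrected in both documents. The conflict with 4.1.1 and 4.3.1.1 is textual and needs no assumption. That the cell is a garbled share of patients is an inference, supported by the match at n = 3. The gap at 3 or 4 of 6 and at 3 of 3 depends on reading the count as patients with adequate exposure, and its frequency (0.10 to 0.59 for 3 or 4 of 6 over p from 0.2 to 0.9) rests on the assumed p.

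The documents do not show that the RP2D was chosen on the wrong criterion; that cannot be judged without the charter and the DRC records. Dose-finding is past, so correcting the tables changes no child's dose. The live consequence is for reporting the primary dose-finding result: as planned, the CSR need not show whether 5 of 6 was met or which rule selected the dose. The sample size and error rates of the expansion phase are not affected.

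**What to change.** 1. In protocol Table 8 and SAP Table 1, replace the cell with: exposure not adequate per 4.1.1 (fewer than 5 of 6 patients at the dose level meet the 50% criterion), leading to the next dose level.
2. State that a cohort smaller than 6 from which 5 of 6 is still reachable is filled to 6 before a PK decision. Refer to this condition in the Arm B sentence of 4.1.1.
3. In the SAP and CSR, report by dose level, weight arm and drug the number of patients who met the 50% criterion as the DRC applied it. Name the source of the 80% limit. The non-compartmental AUC planned in SAP 3.4.1 and 4.2.4.1 gives no confidence interval per patient, so the limit would have to come from elsewhere, for example the population PK model of SAP 4.2.4.2. Say also whether the bound was per patient, as 5 of 6 implies, because 4.3.1.1 refers to the current dose level and leaves this open.
4. State in the CSR which rule selected the RP2D, and cite the DRC charter if it already holds the correct rule.

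The cost is wording in two tables and one paragraph, one additional PK output and a sentence in the CSR. The output is not free if the 80% limits must be taken from a separate model report. Under the filling rule, a cohort started at 3 would need up to 3 more children at that level; with dose-finding past, that cost would arise only if the rule were used again.
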